13.3.2 Unexpected Adverse Events

(Notify sponsor or designee by the next business day; document on eCRF)

An unexpected AE is any adverse drug event that is not identified in nature, severity, or frequency in the current protocol, IB or in other reports or information provided to the investigator. This refers to any AE that has not been previously observed, (eg, included in the IB), rather than from the perspective of such an event not being anticipated from the pharmacological properties of the product. For example: hepatic necrosis would be unexpected (by virtue of greater severity) if the Investigator brochure only referred to elevated hepatic enzymes or hepatitis. Unexpected adverse events may or may not be serious.

13.3.3 Non-Serious Adverse Events

(Document on eCRF)

All other AEs, not fulfilling the previous definitions, are classified as non-serious.

13.3.4 Protocol-Related Adverse Events

AEs that are not related to KD019 may be considered by the investigator or the medical monitor to be related to the conduct of the clinical study. That is, the event may be related to the fact that a subject is participating in the study. For example, a protocol-related AE may be an event that occurs during a washout period or that is related to a procedure required by the protocol.

13.3.5 Relationship/Causality to Study Drug

The investigator will assess the relationship of the event to study drug as (1) not related; (2) unlikely related; (3) possibly related; (4) probably related; or (5) definitely related.

In assigning the causal relationship, the following should also be considered:

- Temporal relationship Did the effect occur in a reasonable temporal association with administration of KD019?
- Pattern consistent with known drug effect Is the effect an expected consequence of KD019 administration based upon the known biologic effects, toxicologic data, and prior experience with KD019 or closely related drugs?
- Other potential etiologies Is there another more likely cause of the adverse effect?

- Challenge Did the adverse event recur or worsen upon re-exposure to KD019 or upon an increase in the dose? (Note: Intentional re-challenge for the purpose of assessing causal relationship of an adverse event to the study drug should NOT be performed.)
- De-challenge Did the adverse event resolve or diminish upon cessation of KD019 treatment or reduction in dose?

13.3.6 Recording Adverse Events

All AEs (including SAEs) are to be accurately recorded on the Adverse Event page of the subject's eCRF and not as remarks elsewhere on the eCRF. The following aspects of the AE must be recorded:

- The onset date and time (when applicable) of the AE
- Intensity/severity (per the Clinical Symptom and Adverse Event Grading Scale, Appendix C)
- The resolution date and time of the AE, when applicable
- A description of the AE
- Any factors considered as possibly promoting the occurrence of the AE
- Concomitant medication/therapy including name, dose, dose frequency, indication, and dates of use
- An assessment of the relationship/causality by the investigator; a decisive factor in the documentation is the temporal relationship between the AE and study drug.

13.3.7 Adverse Event Monitoring and Follow-Up

The investigator will follow all subjects who experience adverse events until the event has resolved or has stabilized (ie, the subject has returned to the baseline state or the investigator does not expect any further improvement or worsening of the subject's condition). The appropriate follow-up visits must be scheduled and the specific tests repeated or performed as necessary. Where a diagnosis is possible, it is preferable to report this diagnosis rather than a series of terms (signs/symptoms) relating to the diagnosis.

13.3.8 Laboratory and ECG Abnormalities

Note: For the purposes of this study, ECG abnormalities will be handled in the same manner as laboratory abnormalities.

Non-Clinically Significant (NCS) Laboratory Abnormalities

All laboratory results must be filed in the subject's medical record and be monitored. The investigator must review laboratory results in a timely manner demonstrated by signature/date and assignment of clinical significance assessment. Non-clinically-significant laboratory abnormalities, ie, minor deviations from the normal range, are expected and it is likely that no medical intervention will be required. Such results will not be considered to be adverse events.

Clinically Significant (CS) Laboratory Abnormalities

CS laboratory abnormalities will be graded using the CTCAE.

All severe and life-threatening laboratory result abnormalities and any laboratory abnormality that is considered to be clinically significant by the investigator will be recorded on the AE eCRF. An abnormal test result will be considered an AE if:

- It is not associated with an already reported AE, diagnosis or pre-existing condition
- There is a change in concomitant medication or intervention as needed, in direct response to the laboratory result
- The investigator exercises his/her discretion to make significance determinations for any subject laboratory result or result that requires intervention

All such lab abnormalities will be repeated and assessed by the investigator, or licensed (MD), as soon as possible for "seriousness" and if they meet the regulatory definition of "serious", they will be reported as SAEs following regulatory and protocol requirements. Repeat laboratory tests may be run in order to monitor the result.

Serious Laboratory Abnormalities

Any lab abnormality meeting the regulatory definition of "serious" must be recorded on both the adverse event eCRF/record and the Serious Adverse Event Form. If a subject experiences a serious toxicity or dies, the FDA will be notified within 24 hours, as required.

13.3.9 Pregnancy

If any subject or the partner of a subject becomes pregnant following the first dose of tesevatinib, the subject will be taken off study. If any subject or a partner of a subject becomes pregnant, the subject and/or their partner will be followed regularly until birth or termination of the pregnancy. The pregnancy must be immediately reported to the sponsor. Forms for reporting pregnancies will be provided to the study sites upon request. The anticipated date of birth or termination of the pregnancy should be provided at the time of the initial report. The outcome of a pregnancy (for a subject or for the partner of a subject) must be reported to the medical monitor as soon as it is known. If the pregnancy ends for any reason before the anticipated date initially reported, the investigator must notify the Kadmon medical monitor as soon as possible.

If the outcome of the pregnancy meets any criterion for classification as a SAE (including stillbirth, neonatal death, spontaneous abortion, or congenital anomaly – including that in an aborted fetus) the investigator must follow the procedures for reporting SAEs. Any neonatal death occurring ≤ 30 days after birth will be reported as a SAE.

13.3.10 Serious Adverse Event Reporting

Governing Regulatory Requirements

Compliance with this request for prompt reporting is essential in that the sponsor is responsible for informing the US Food and Drug Administration (FDA) and other regulatory authorities as well as all other participating investigators of the event.

Under FDA ruling (US Code of Federal Regulations, Title 21 CFR Part 312.32) and the ICH Guidelines for Clinical Safety Data Management Definitions and Standards for Expedited Reporting, the sponsor is required to submit written documentation, in the form of a safety report, detailing:

- Any event associated with the use of the drug, that is both serious and unexpected, or
- Any finding from tests in laboratory animals that suggests a significant risk for human subjects, including reports of mutagenicity, teratogenicity, or carcinogenicity

Written submission must be made by the sponsor to the FDA and the IRBs as soon as possible and in no event later than 15 calendar days after the sponsor's initial notification of the event. The sponsor shall also inform all investigators.

In addition, the sponsor is further required to report, by either telephone or facsimile transmission or in writing to the FDA the occurrence of any unexpected fatal or life-threatening event associated with the use of the drug and no later than 7 calendar days after notification of the event.

Time-Frame for Reporting

Any death, pregnancy, or SAE experienced by a patient from the time of informed consent until 30 days after receiving the last dose of study drug, regardless of relationship to study drug, or any death that occurs more than 30 days after receiving study drug, and is believed to be study drug-related, must be promptly reported (within 24 hours of the investigator becoming aware of the event) by fax to the sponsor (or designee).

In the event of an issue with the fax line, forward the SAE form via email to [contact].

The investigator will be able to contact the safety Medical Monitor at all times:

Information to be Provided by the Investigator

SAEs must be recorded on the SAE eCRF page. This requirement includes all SAEs that occur after informed consent and through 30 days after last dose of study treatment, and in addition, any SAE that are assessed as possibly related to study treatment by the investigator, even if the SAE occurs more than 30 days after the last dose of study treatment.

The minimum information required for SAE reporting includes identity of investigator, site number, subject number, an event description, SAE term(s), onset date, the reason why the event is considered to be serious (ie, the seriousness criteria) and the investigator's assessment of the

relationship of the event to study treatment (not related, unlikely related, possibly related, probably related, or definitely related). Additional SAE information including medications or other therapeutic measures used to treat the event, action taken with the study treatment due to the event, and the outcome/resolution of the event will be recorded on the SAE form. Forms for reporting SAEs will be provided to the study sites.

In all cases, the investigator should continue to monitor the clinical situation and report all material facts relating to the progression or outcome of the SAE. Furthermore, the investigator may be required to provide supplementary information as requested by the Kadmon Drug Safety personnel or designee.

When reporting SAEs, the following additional points should be noted:

- When the diagnosis of an SAE is known or suspected, the investigator should report the diagnosis or syndrome as the primary SAE term, rather than as signs or symptoms. Signs and symptoms may then be described in the event description. For example, dyspnea should not be used as an SAE term if the diagnosis which caused the dyspnea is known to be malignant pleural effusion.
- Death should not be reported as an SAE, but as an outcome of a specific SAE. The cause of death is the SAE. In the exceptional case where the events leading to death are unknown, then death may be used as an event term. If an autopsy was performed, the autopsy report should be provided.
- While most hospitalizations necessitate reporting of an SAE, some hospitalizations do not require SAE reporting, as follows:
 - Elective or previously scheduled surgery, (eg, a previously scheduled ventral hernia repair)
 - Procedures for pre-existing conditions that have not worsened after initiation of treatment
 - Pre-specified study hospitalizations for observation
 - Events that result in hospital stays of less than 24 hours and that do not require admission, (eg, an emergency room visit for hematuria that results in a diagnosis of cystitis and discharge to home on oral antibiotics)
- SAEs must, however, be reported for any surgical or procedural complication resulting in prolongation of the hospitalization.

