 - Sexually active women of childbearing potential enrolled in the study must agree to use two forms of accepted methods of contraception during the course of the study and for 6 months after their last dose of study drug. Effective birth control includes (a) IUD plus one barrier method; (b) on stable doses of hormonal contraception for at least 3 months (eg, oral, injectable, implant, transdermal) plus one barrier method; or (c) 2 barrier methods. Effective barrier methods are male or female condoms, diaphragms, and spermicides (creams or gels that contain a chemical to kill sperm); or (d) a vasectomized partner
- 11. For male subjects who are sexually active and who are partners of premenopausal women: agreement to use two forms of contraception as in criterion 10 above during the treatment period and for at least 6 months after the last dose of study drug.

12. The subject has no history of another malignancy in the 5 years prior to study entry, except treated non-melanoma skin cancer or superficial bladder cancer or carcinoma in-situ of the cervix or Stage 1 or 2 cancers of other sites that have been treated surgically and have not recurred.

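### The protocol's two pregnancy-reporting rules conflict with each other, and the only one with an end date stops well before the protocol's own 6-month contraception period does

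*Protocol*

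**What the plan says.** Four parts of the protocol bear on this.

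- **Contraception (Section 8.2, repeated in the synopsis).** Under criterion 10, sexually active women of childbearing potential must use two methods "during the course of the study and for 6 months after their last dose of study drug". Under criterion 11, sexually active men with premenopausal partners must do so during treatment and "for at least 6 months after the last dose of study drug".
- **Pregnancy (Section 13.3.9).** "If any subject or the partner of a subject becomes pregnant following the first dose of tesevatinib, the subject will be taken off study". The section then requires follow-up of the subject or partner until birth or termination, and adds: "The pregnancy must be immediately reported to the sponsor". Adverse outcomes such as stillbirth or congenital anomaly go through the SAE procedures. No end date is given.
- **Reporting time-frame (Section 13.3.10).** Sites must report within 24 hours "Any death, pregnancy, or SAE experienced by a patient from the time of informed consent until 30 days after receiving the last dose". The same sentence reaches further only for death: "or any death that occurs more than 30 days after receiving study drug, and is believed to be study drug-related". Later in the section, possibly related SAEs also remain reportable after 30 days. Pregnancy is not extended, and partners are not mentioned.
- **Follow-up (Sections 9.7 and 11.1).** Subjects are followed for 30 days after the last dose. The last scheduled pregnancy test is at the End-of-Study visit, 30 ± 3 days after the last dose.

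**The concern.** A site that asks how long it must report pregnancies, and whose, gets two different answers from adjacent sections. One is open-ended and includes partners. The other carries an explicit limit of 30 days and names only the patient. Neither is tied to the 6 months for which the protocol requires contraception.

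At stake is the completeness of pregnancy and outcome data for this drug. A pregnancy that begins after the End-of-Study visit but within the contraception period is one the protocol has asked subjects to prevent. Whether the sponsor hears of it depends on which section the site follows and on whether the subject volunteers the information.

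**Working it through.** The protocol states no figure to reproduce. The check sets the rules side by side and then takes one difference.

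| Rule | Who | Starts | Ends |
|---|---|---|---|
| 8.2, criterion 10 | Women of childbearing potential | During the study | 6 months after last dose |
| 8.2, criterion 11 | Men with premenopausal partners | During treatment | At least 6 months after last dose |
| 13.3.9 (report immediately) | Subject or partner | After first dose | Not stated |
| 13.3.10 (report within 24 hours) | Patient only | Informed consent | 30 days after last dose |
| 9.7 and 11.1 (last planned contact) | All subjects | – | About 30 days after last dose |

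**Where the two reporting rules disagree**

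1. A female subject conceives after Day 30 but within 6 months of the last dose. Section 13.3.9 requires a report; the time-frame in 13.3.10 does not reach it.
2. A male subject's partner becomes pregnant, at any time after his first dose. Section 13.3.9 requires a report; the event is outside the wording of 13.3.10, which speaks of what a patient experiences.
3. A subject becomes pregnant between consent and first dose. Section 13.3.10 covers it; the opening sentence of 13.3.9 starts only at the first dose.

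**Distance between the two stated periods**

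The protocol gives no day count for 6 months, so I assume 168 days (6 × 28) to 184 days (six calendar months at their longest).

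- Shorter: 168 − 30 = 138 days.
- Longer: 184 − 30 = 154 days.

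So the limit in 13.3.10 falls about 5 months before the contraception period ends. Under 13.3.9 as written, the corresponding figure is 0 days, because that duty has no end.

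**Means of detection**

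After the End-of-Study visit the protocol body plans no visit, test or call, and it contains no instruction to subjects to report a later pregnancy. Even on the broad reading of 13.3.9, a site would learn of such a pregnancy only if told.

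**The case against.** The strongest reply is that 13.3.9 is the dedicated pregnancy section and already does the work. It covers partners, has no end date, and requires an immediate report, follow-up to birth or termination, and SAE handling of adverse outcomes. Section 13.3.10 is the time-frame for SAE reporting and does not say that it limits 13.3.9. A site that reads both should report a late pregnancy. Removal from study, which opens 13.3.9, makes sense only for someone still on study, but the follow-up and reporting sentences come after it and carry no such condition. This reply largely stands, and it rules out three stronger readings.

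- **That most of the post-treatment risk period is not captured.** A reader might divide 138/168 or 154/184 and conclude that 82–84% of the period is lost. That share applies only to 13.3.10 read alone.
- **That a known number of women is affected.** A reader might carry the sex mix in Table 5-1 over to the SILK cohort. The documents give neither childbearing potential nor an expected number of pregnancies, and SILK is selected on different criteria, so the result would not count anyone affected.
- **That meaningful drug exposure persists through months 2 to 6.** The protocol gives no reason for choosing 6 months. Its half-lives of 50 to 92 hours (Section 5.2.2.3) put 30 days, or 720 hours, at 720/92 = 7.8 to 720/50 = 14.4 half-lives, leaving under 0.5% of the drug. The 6 months may rest on another basis, but the documents do not show it.

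Finally, the consent pages are not in the copy reviewed. An instruction to report later pregnancies may be there, so only its absence from the protocol body can be stated.

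What the reply does not remove is the conflict. The only explicit end date for pregnancy reporting is 30 days, it stands in the section that sets the 24-hour clock, and no planned contact supports the longer duty.

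**Conclusion.** The concern holds as an inconsistency in safety reporting. Sections 13.3.9 and 13.3.10 differ on who is covered, when the duty starts and when it ends. The one stated end date falls about 138 to 154 days before the end of the protocol's own contraception period. A site relying on 13.3.10 could miss a reportable subject or partner pregnancy; a site following 13.3.9 literally would not, provided it was told of the pregnancy.

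The day range rests on taking 6 months as 168 to 184 days. The statement about absent contact rests on the protocol body alone. I take no position on how long contraception should last; the point is only that the protocol's own periods do not agree. It bears on the completeness of safety data and not on sample size, any endpoint or any analysis. It is worth correcting at the next amendment.

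**What to change.** Reconcile Sections 13.3.9, 13.3.10 and inclusion criteria 10 and 11:

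- In 13.3.10, state the pregnancy time-frame separately from that for deaths and SAEs. It should name both subjects and partners, keep its start at informed consent, and be no shorter than the contraception period in criteria 10 and 11.
- Cross-refer the two sections, and say that the 24-hour time-frame does not narrow the open-ended duty in 13.3.9. A window running from first dose to a fixed end would shorten 13.3.10 at its start and put a cap on 13.3.9, so that wording should be avoided.
- At the existing End-of-Study visit (Section 9.7), tell subjects to report later pregnancies, including a partner's, to the site. Check that the consent form says the same.

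The cost is a few sentences in an amendment and one instruction at a visit already planned. No visit or test is added. The downside is that sites must accept passive reports for about 5 more months.

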13.3.11 Regulatory Reporting

Kadmon Drug Safety (or designee) will process and evaluate all SAEs as soon as the reports are received. For each SAE received, Kadmon will make a determination as to whether the criteria for expedited reporting have been met.

Kadmon (or designee) will submit SAEs that meet the criteria for expedited reporting to the Regulatory Authorities in accordance with local regulations governing safety reporting. Reporting of SAEs by the investigator to his or her IRB will be done in accordance with the standard operating procedures and policies of the IRB. Adequate documentation must be maintained showing that the IRB was properly notified.

13.3.12 Follow-up Information on a Serious Adverse Event

Appropriate diagnostic tests should be performed and therapeutic measures, if indicated, should be instituted. Appropriate consultation and follow-up evaluations should be carried out until the event has returned to baseline or is otherwise explained by the investigator.

Follow-up data concerning the SAE (eg, diagnostic test reports, physician's summaries, etc.) also must be submitted to Kadmon, as they become available, by telefax or email transmission, until resolution of the SAE.

13.4 Other Safety Considerations

13.4.1 Medication Errors

Any medication error that results in an AE, even if it does not meet the definition of serious, requires reporting within 24 hours to the medical monitor. An overdose of tesevatinib without any associated signs or symptoms, unless the subject is hospitalized for observation, will not constitute an AE but will be recorded as a protocol deviation.

13.4.2 Follow-Up of Serious Adverse Events

Any SAE that led to treatment discontinuation (including clinically significant abnormal laboratory values that meet these criteria) and is ongoing 30 days after last dose of study treatment must be followed until the event has resolved or has stabilized (ie, the subject has returned to the baseline state, or the investigator does not expect any further improvement or worsening of the subject's condition). This follow-up guidance also applies to SAEs that occur more than 30 days after last dose of study treatment.

13.5 Safety Monitoring

To minimize the possibility of exposing study subjects to unusual risk, at the end of each dosing cohort, the safety information from this study will be reviewed by an independent Data Safety Committee, including an independent safety monitor with clinical expertise in PKD and an independent cardiologist. Safety data will be reviewed, and a recommendation will be made to the study sponsor as to whether it is safe to proceed to the next dosing cohort.

